## 5 INTRODUCTION

### 5.1 Investigational Medicinal Product

A4250 is a small molecule and a potent selective inhibitor of the ileal bile acid transporter (IBAT), also known as the apical sodium-dependent bile acid transporter (ASBT). IBAT is an integral brush border membrane glycoprotein that co-transporters sodium and bile acids and appears to be a critical component in the regulation of the bile acid pool size in animals and man. This transporter, expressed in the distal ileum, is a key element in the enterohepatic circulation of bile acids since it facilitates the high-affinity, high-capacity reabsorption of bile acids. Indeed, 95% of secreted bile acids are reabsorbed via IBAT [Hofmann 2009; Miethke 2016]. A4250 is orally administered and acts locally in the gut where it binds reversibly to IBAT to decrease the reuptake of bile acids. A4250 has minimal systemic exposure at the predicted therapeutic dose ranges.

No safety signals were found with A4250 in preclinical safety and toxicity studies. In the first clinical study of A4250 in healthy volunteers, A4250 was given as a single oral dose up to 10 mg or daily oral doses up to 3 mg/day for 7 days. A4250 was well tolerated and the only findings were gastrointestinal (GI) related effects, such as diarrhea, at higher doses.

In an exploratory Phase 2 study in children with cholestatic pruritus, A4250 was given as oral doses of 10 to 200 µg/kg/day for 4 weeks. A4250 reduced mean levels of serum bile acids (s-BA) in all cohorts. In 11 of 13 progressive familial intrahepatic cholestasis (PFIC) patients, substantial reductions (ranging from 43% to 98%) were observed. Patient-reported diary data documented improvement of pruritus during treatment. A4250 was well tolerated. No serious adverse events (SAEs) were deemed to be related to study drug, and most adverse events (AEs), including some increased transaminases, were considered unrelated to study drug and transient in nature.

### 5.2 Background

#### 5.2.1 Progressive Familial Intrahepatic Cholestasis

PFIC is a rare autosomal recessive cholestatic liver disease estimated to affect between 1 in every 50,000 to 100,000 children born worldwide. PFIC represents 10% to 15% of causes of cholestasis in children and 10% to 15% of liver transplantation indications in children. All types of PFIC exist worldwide and both sexes appear to be equally affected.

The common underlying pathogenesis of PFIC is disruption of bile formation and bile transport through the liver [Jacquemin 2000]. The classification of PFIC has evolved over the years. The most commonly used sub-classifications are PFIC Types 1, 2, and 3, which are based on the associated affected gene and described in more detail below.

- PFIC, Type 1: also referred to as “Byler disease” or “familial intrahepatic cholestasis-1 (FIC1) protein deficiency.” FIC1 protein is located on the canalicular membrane of hepatocytes and facilitates movement of aminophospholipids from the outer

to inner leaflet of the plasma membrane of the hepatocyte. The *ATP8B1* gene encodes FIC1 protein. Biallelic pathologic variants in the *ATP8B1* gene are associated with FIC1 dysfunction and classified clinically as PFIC Type 1 disease.

- PFIC, Type 2: also referred to as “Byler syndrome” or “bile salt export pump (BSEP) deficiency.” BSEP is a transporter protein that is expressed at the canalicular membrane of hepatocytes, and is the primary exporter of bile acids. The *ABCB11* gene encodes the BSEP protein. Biallelic pathologic variations in the *ABCB11* gene are associated with BSEP dysfunction and classified clinically as PFIC Type 2 disease.
- PFIC, Type 3: is caused by a deficiency of the multidrug-resistance protein 3 (MDR3) due to mutations in the *ABCB4* gene. MDR3 is a phospholipid translocase critical for phospholipid secretion.

Severe pruritus is common in children diagnosed with PFIC. Itching (and subsequent scratching) is a significant morbidity for these patients and their families [Suchy 2007]. A more severe degree of pruritus is experienced compared to patients with other forms of liver disease and to other pruritic conditions such as atopic dermatitis [Murray 2011]. In patients with PFIC, liver biopsy reveals canalicular cholestasis and, later, the appearance of portal fibrosis. Serum biochemistry indicates cholestasis with hyperbilirubinemia, elevated alanine aminotransferase (ALT) and aspartate aminotransferase (AST). The concentrations of bile acids in serum are very high, while serum gamma-glutamyl transferase activity (exception being MDR3 variants) and cholesterol are normal [Hori 2010]. Symptoms of portal hypertension and liver failure will develop during the course of the disease [Davitt-Spraul 2009; Alissa 2008]. Symptoms develop early; median age at onset of symptoms is 2 months, and 78% of PFIC patients present with jaundice [Pawlikowska 2010]. The life-threatening and debilitating nature of PFIC is reflected by the fact that survival in those not resorting to surgery is 50% at 10 years of age and almost zero at 20 years of age. Approximately half of PFIC patients undergo liver transplantation [Davitt-Spraul 2009] and treatment-resistant pruritus is the leading indication for the surgical procedure partial external biliary diversion, mostly in PFIC Type 1 and 2 patients.

PFIC is life-threatening and debilitating. Currently, the treatment for PFIC is palliative and there is no pharmaceutical treatment approved for use in PFIC. The therapeutic choices are restricted to non-specific therapy of the symptoms and signs of the disease such as nutritional support, preventing vitamin deficiencies, and treatment of extrahepatic features. Medical treatment options include off-label use of ursodeoxycholic acid, rifampin, antihistamines, and naltrexone. A minority of patients respond nominally and transiently to these interventions. Biliary diversion is used to decrease systemic bile acids through interruption of the enterohepatic circulation and so avoid transplantation. Liver transplantation is typically only viewed as an option when patients have failed medical treatment and/or biliary diversion and have liver failure or persistent uncontrolled pruritus.

## 5.2.2 Summary of Clinical and Nonclinical Studies

This is a summary of nonclinical and clinical studies. More detail is provided in the Investigator's Brochure ([IB] see [A4250 IB](#)).

A4250 is a potent, selective IBAT inhibitor with no safety signals seen in the safety pharmacological studies. In addition, no safety signals were seen in repeat-dose oral toxicity studies in rats with up to 26 weeks of daily dosing and in dogs with up to 39 weeks of daily dosing. No safety signals were identified when A4250 was administered daily to juvenile rats from age 14 days to 63 days.

A4250 is minimally absorbed with very low systemic exposure in both humans and other species. In blood, protein binding is high (>99.7%). Systemically absorbed A4250 is slowly metabolized in humans and in preclinical studies by hydroxylation only, a metabolite that retains IBAT activity. A4250 did not show any significant inhibition of cytochrome P450 (CYP) enzymes in the rat. A4250 inhibited human CYP3A4 and CYP2D6 (IC50: 16 µmol/L for both enzymes), and CYP2C9 (IC50: 1.2 µmol/L).

To date, A4250 has been studied in 3 Albireo-sponsored clinical studies: a study in healthy volunteers evaluating single and multiple administration of A4250; a single-dose absorption, distribution, metabolism, and excretion (ADME) study; and a Phase 2 study in children with cholestatic pruritus. In addition, an investigator-sponsored study has been conducted in patients with primary biliary cholangitis (PBC). In total, 98 subjects have been exposed to A4250.

In the first clinical study (A4250-001), A4250 was given to healthy volunteers as a single oral dose up to 10 mg or daily oral doses up to 3 mg/day for 7 days. Following a single oral dose of 10 mg, the median maximum drug concentration was 0.2 nmol/L and the area under the curve was 0.8 nmol × h/L (n=6). Pharmacodynamic evaluation of bile acid synthesis biomarkers (serum fibroblast growth factor 19 [s-FGF19] and plasma 7α Hydroxy 4-cholesten-3-one [p-C4]) identified the expected decrease in s-FGF19 and an increase in p-C4. In addition, total plasma bile acids decreased and total fecal bile acids increased in A4250-treated patients compared to placebo. A4250 was generally well tolerated. The only findings were GI-related effects, such as diarrhea at higher doses.

In the ADME study (A4250-007), healthy subjects were administered a single oral dose of 3 mg [C]-A4250 capsule. The main excretion route was determined to be fecal. There were no quantifiable concentrations of A4250 in plasma or total radioactivity in plasma or whole blood. A4250 was well tolerated. AEs were reported and most were mild and not related to A4250. The 3 AEs experienced by 2 subjects reported as related to study drug were GI in nature, including diarrhea (2 AEs; 2 subjects) and abdominal pain (1 AE; 1 subject).

In an exploratory Phase 2 study in children with cholestatic pruritus (A4250-003), A4250 was administered as oral daily doses of 0.01 to 0.2 mg/kg for 4 weeks. Twenty patients (8 females and 12 males) aged 1 to 17 years were enrolled in this open-label dose-escalation study. Four patients were re-enrolled into a second dose level. No

treatment-related SAEs were reported, and most AEs, including some increased transaminases, were transient. Four-week, once-daily treatment with A4250 reduced mean levels of s-BA in all cohorts. Substantial s-BA reductions in 11 of 13 PFIC patients (ranging from 43% to 98%) were observed. A4250 also reduced s-BA in the 11 non-PFIC patients, but to a lesser extent than in PFIC patients. Patient-reported diaries documented improvement of the visual analogue scale itch score in 17 of 24 patients during treatment. The dose with the greatest improvement showed a mean decrease ( $\pm$  standard error of the mean) of  $2.9 \pm 1.1$  from baseline. The results from this study form the basis of the current (A4250-005) study design.

### 5.3 Rationale

In this investigational study, A4250 is under development for treatment of PFIC and is also being considered for other orphan cholestatic liver diseases.

There is currently no medical treatment approved for PFIC. In PFIC patients with severe pruritus, biliary diversion surgery is used to decrease systemic bile acids through interruption of the enterohepatic circulation and thereby reducing pruritus [Whittington 1988]. Liver transplantation is typically used as an option when patients have failed medical treatment and/or biliary diversion and have liver failure or persistent uncontrolled pruritus.

By inhibiting IBAT with high selectivity and potency, A4250 has the potential to relieve cholestasis and improve liver function without surgical intervention in patients with PFIC. Since A4250 is minimally absorbed and achieves a substantial reduction of s-BA, it has the potential to be a safer and less invasive alternative to surgical biliary drainage. The rationale for using A4250 is to decrease s-BA levels, and to reduce the major morbidity of pruritus, improving the health and wellbeing of patients affected with PFIC. Ultimately, this noninvasive therapeutic approach has the potential to not only improve quality of life (QoL), but also reduce the need for biliary diversion and subsequent liver failure and liver transplantation.

The doses selected, 40 and 120  $\mu\text{g}/\text{kg}/\text{day}$ , were based on the efficacy and safety data generated from patients with PFIC ( $n=10 + 3$  re-entered) and supporting data from all patients ( $n=20 + 4$  re-entered) in the five dose groups dosed in the A4250-003 study. Improvements in s-BA and pruritus were observed with doses from 30  $\mu\text{g}/\text{kg}$  to 100  $\mu\text{g}/\text{kg}$ , with a dose-related trend. The best dose response in all patients was at the 60  $\mu\text{g}/\text{kg}/\text{day}$  for s-BA and 100  $\mu\text{g}/\text{kg}/\text{day}$  for pruritus. The best dose response in the PFIC subgroup was at 30  $\mu\text{g}/\text{kg}/\text{day}$  for both s-BA and pruritus. Patients with PFIC responded well to the doses given from 30  $\mu\text{g}/\text{kg}$  to 200  $\mu\text{g}/\text{kg}$ ; however, a clear dose relationship could not be established in order to select a single dose for this Phase 3 study. As efficacy was observed at both low and high doses, 40  $\mu\text{g}/\text{kg}$  and 120  $\mu\text{g}/\text{kg}/\text{day}$  are considered to be the most optimal for this study.

This study will be conducted in compliance with the protocol and with the International Council for Harmonisation (ICH) guidelines on Good Clinical Practice (GCP).

Patients completing 24 weeks of double-blind treatment will be offered to enter Study A4250-008 and receive open-label treatment with A4250.

### **5.3.1 Risk/Benefit**

A4250 has been evaluated in three Albireo-sponsored clinical studies: a double-blind placebo-controlled study in healthy volunteers, a single-dose ADME study, and a Phase 2 study in children with cholestatic pruritus. In addition, an investigator-sponsored study has been conducted in patients with PBC.

A total of 98 subjects/patients have been exposed to A4250. Healthy subjects have been exposed to up to 10 mg as a single dose and up to 3 mg daily as part of a multiple-dose evaluation. Children with cholestatic liver disease have been treated with up to 0.2 mg/kg/day (200 µg/kg/day) for 4 weeks. In total, 2 SAEs have been reported; both were judged by the physician to be not related to the study drug.

Patients with cholestatic liver diseases suffer from excess bile acids in the liver resulting in tissue damage. A commonly used treatment in these patients is bile diversion surgery, whereby approximately 50% to 100% of the enterohepatic circulation of bile acids is interrupted. Inhibition of IBAT with A4250, thereby interrupting the enterohepatic circulation of bile acids, is therefore a potential medical alternative to surgery which could be of benefit to these patients if shown to be effective and safe. Data from the Phase 2 study showed efficacy of A4250 in reducing s-BA concentrations and pruritus in such patients.

Based on the mode of action of an IBAT inhibitor, loose stools or diarrhea could be expected. However, in the pediatric Phase 2 study with 4 weeks daily treatment, only one patient had mild transient diarrhea after a single dose that did not recur on multiple dosing.

## **6 STUDY OBJECTIVES**

### **6.1 Primary Objectives**

To demonstrate the efficacy of repeated daily doses of 40 µg/kg/day and 120 µg/kg/day A4250 in children with PFIC Types 1 and 2, as determined by the following:

- The proportion of patients experiencing at least a 70% reduction in fasting s-BA concentration from baseline to end of treatment or reaching a level  $\leq 70$  µmol/L compared to placebo after 24 weeks of treatment
- Change from baseline to Week 24 in pruritus compared to placebo

### **6.2 Secondary Objectives**

- To evaluate the effect of A4250 on serum ALT concentration
- To evaluate the effect of A4250 on growth
- To evaluate the effect of A4250 on sleep disturbance
- To evaluate the effect of A4250 on the need for surgical treatment (biliary diversion or liver transplantation)
- To assess the safety and tolerability of repeated daily doses of A4250 for 24 weeks

## 7 INVESTIGATIONAL PLAN

### 7.1 Overall Study Design and Plan

#### 7.1.1 Description

This is a double-blind, randomized, placebo-controlled, Phase 3 study to investigate the efficacy and safety of 40 µg/kg/day and 120 µg/kg/day of A4250 compared to placebo in children with PFIC (deficiencies of FIC1 or BSEP).

Study data will be periodically reviewed by an unblinded Data Safety and Monitoring Board (DSMB).

The study includes a 35- to 56-day Screening Period followed by a 24-week Treatment Period and a 4-week Follow-Up Period.

After completion of the Screening Period, eligible patients (20 per treatment group) will be randomized on Day 0 (Visit 3) in a 1:1:1 fashion to receive 40 µg/kg/day or 120 µg/kg/day of A4250, or a matching placebo.

Patients who complete the Treatment Period and Visit 9 (Day 168) in this study will be invited to participate in a 72-week open-label extension study (A4250-008, EudraCT Number 017-002325-38, subject to a separate study approval) in which all patients will receive active treatment. A patient who prematurely withdraws due to no improvement/intolerable symptoms, and has completed at least 12 weeks of the Treatment Period and End of Treatment (EOT) Visit, will also be offered the opportunity to enter Study A4250-008.

Visit windows applicable to each visit are presented in the schedule of assessments ([Table 1](#)). There will be up to 10 clinic visits during the study ([Figure 1](#)) and one scheduled telephone contact, as follows:

- Visit 1: Screening Period start. Patient is considered enrolled after signing the informed consent form (ICF) (Days -56 to -35)
- Visit 2: second Screening Visit (Days -28 to -7)
- Visit 3: Randomization Visit (Day 0)
- Telephone Contact 1: (Day 14)
- Visit 4: Clinic Visit (Day 28)
- Visit 5: Clinic Visit (Day 56)
- Visit 6: Clinic Visit (Day 84)
- Visit 7: Clinic Visit (Day 126)
- Visit 8: Clinic Visit (Day 154)
- Visit 9: Clinic Visit, EOT (Day 168)

- Visit 10: Follow-Up Visit, 28 days after last dose of study drug (Day 196). All patients continuing in Study A4250-008 will not have this Follow-up Visit.

Additional clinic visits may be required for patients who need direct site assistance, e.g., due to AE monitoring, to fulfil screening requirements, and/or for safety maintenance.

### **Screening Period**

Informed consent must be obtained at Visit 1 prior to performing any study procedures. After signing the ICF, patients will be considered enrolled and evaluated for study eligibility.

Daily recording of pruritus using an electronic diary (eDiary) will be started to determine confirmation of the magnitude and the baseline pruritus symptoms before the study. After consultation with the Medical Monitor, patients failing eligibility criteria may be re-screened after 2 months. Patients not fulfilling inclusion/exclusion criteria after 3 attempts are not allowed to re-screen.

Caregivers/patients will be instructed on the daily use of the eDiary. The eDiary will include patient-reported outcome (PRO) and observer-reported outcome (ObsRO) items for evaluation of itching (PRO), scratching (ObsRO), and sleep disturbance (PRO and ObsRO) during the Screening Period (study Days -56 to 0) and throughout the 24-week Treatment Period (study Days 0 to 168).

Only the 14 most recent days before randomization will be used for eligibility calculation of the diary entries. Observer-reported outcomes in patients of all ages will be recorded by a caregiver (or caregiver's designee). If possible, the same caregiver will complete the Albireo ObsRO items throughout the study.

At a second Screening Visit (Visit 2) additional laboratory samples will be taken for eligibility assessments.

### **Treatment Period**

Eligibility for randomization will be determined at Visit 3 using the pruritus (scratching reports from the Albireo ObsRO) data in the 2 weeks before Visit 3, genetic confirmation of diagnosis, and the liver biochemistry evaluations from the previous screening visits. Two weeks after Visit 3, there will be a telephone contact with the caregiver/patient to evaluate any AEs.

[figure not shown]
The patient will return to the clinic at Visit 4, Visit 5, Visit 6, Visit 7, Visit 8, and Visit 9 for assessments. If a new caregiver will begin to complete the Albireo ObsRO during the course of the trial, they will be provided with training during a clinic visit before they begin to use the eDiary. Additionally, caregivers/patients will be requested to use the diary to report the date and time each dose of study drug is administered during the Treatment Period.

The last dose of study drug will be administered the day before Visit 9. At study Visit 9, the patient has the option to enroll in an open-label extension study (A4250-008) should they meet the required entry criteria. If the patient is continuing into Study A4250-008 this will be

the last visit in this study and the first visit in Study A4250-008. Visit 9/EOT should also be performed at the time patients are prematurely withdrawn from the study.

Clinic Visit 10 will take place 28 days after Visit 9 for all patients not continuing into Study A4250-008.

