### 7.1.3 Study Procedures and Assessments

#### 7.1.3.1 Screening Period (Days -56 to 0)

##### Day -56 to Day -35/Clinic Visit 1

Patients will undergo a Screening Visit up to 56 days prior to the planned first day of study treatment. Screening procedures and assessments are as follows:

- Obtain written informed consent
- Assess inclusion/exclusion criteria ([Section 7.2](#))
- Record demographics (age, full date of birth, gender, race, and ethnicity)
- Document concomitant medications
- Medical and surgical history (date of diagnosis of PFIC Types 1 or 2, prior investigational medications for PFIC, historical liver function test [LFT] values, any surgery performed, any other diagnosis, and historical liver biopsy data)
- Blood sample for genetic testing
- Collect, if available, past confirmatory clinical genetic laboratory report for PFIC1/PFIC2 and send to central reader for review
- Physical examination, including voluntary photography ([Section 10.2.5](#))
- Skin examination ([Section 10.2.5](#))
- Vital signs ([Section 10.2.6](#))
- eDiary training and compliance requirements; patients begin daily recording of pruritus using the eDiary ([Appendix 2](#))
- Clinical chemistry ([Section 10.2.1](#))
- s-BA ([Section 9.2.1](#))
- Serum pregnancy test for girls of who have reached menarche
- AE monitoring

##### Day -28 to Day -7/Clinic Visit 2

A second Screening Visit will be performed. Screening procedures and assessments are as follows:

- Review concomitant medications
- Vital signs ([Section 10.2.6](#))
- Albireo PRO/ObsRO eDiary review for itching, scratching, and sleep scores and compliance
- Urinalysis ([Section 10.2.1](#))

- s-BA ([Section 9.2.1](#))
- International normalized ratio (INR)
- Fat-soluble vitamins A and E
- Urine pregnancy test for girls of who have reached menarche
- AE monitoring

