12. Serum ALT  $>10 \times$  upper limit of normal (ULN) at Screening
13. Serum ALT  $>15 \times$  ULN at any time point during the last 6 months unless an alternate etiology was confirmed for the elevation
14. Total bilirubin  $>5 \times$  ULN at Screening
15. Patient suffers from uncontrolled, recalcitrant pruritic condition other than PFIC. Examples include, but not limited to, refractory atopic dermatitis or other primary pruritic skin diseases
16. Any patient who is pregnant or lactating or who is planning to become pregnant within 24 weeks of randomization
17. Sexually active males and females who are not using a reliable contraceptive method with  $\leq 1\%$  failure rate (such as barrier protection, hormonal contraception, intrauterine device, or complete abstinence) throughout the duration of the study (from signed informed consent through Follow-up, Visit 10).
18. Patient with a past medical history of alcohol or substance abuse will be excluded. Patient must agree to refrain from illicit drug and alcohol use during the study
19. Administration of bile acid or lipid binding resins and medications that slow GI motility (Refer to [Appendix 1](#) – Concomitant Medications Prohibited during the study)
20. Patient has had investigational exposure to a drug, biologic agent, or medical device within 30 days prior to Screening, or 5 half-lives of the study agent, whichever is longer
21. Patient who has been previously treated with an IBAT inhibitor whose pruritus has not responded to treatment
22. Any other conditions or abnormalities which, in the opinion of the investigator or Medical Monitor, may compromise the safety of the patient, or interfere with the patient participating in or completing the study

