**If any ONE of the following criteria are met:**

1. Transaminases (ALT or AST  $\geq 3 \times$  baseline or 800 U/L, whichever comes first) AND bilirubin (total bilirubin  $> 2 \times$  ULN) elevations
2. Transaminase elevations alone (ALT or AST  $> 10 \times$  ULN or  $5 \times$  baseline or absolute threshold of 800 U/L, whichever comes first) in presence of normal LDH and CPK
3. Cholestatic marker elevations (alkaline phosphatase [ALP] or gamma-glutamyl transferase  $> 2 \times$  baseline) without alternative explanation
4. Total bilirubin increased, unrelated to hemolysis (elevated reticulocyte count) or established genetic diseases, such as Gilbert's syndrome
  - a. Doubling if total bilirubin was  $< 3$  mg/dL at baseline
  - b. OR Increase by  $> 3$  mg/dL if total bilirubin was  $\geq 3$  mg/dL at baseline
5. INR increase refractory to vitamin K administration
  - a. Increase by  $> 1.5$  if INR was normal at baseline
  - b. OR Increase by  $> 0.4$  if INR was abnormal at baseline
6. Any increase in total bilirubin and transaminases if accompanied by EITHER a symptom of clinical hepatitis (e.g., vomiting, nausea, right upper quadrant pain) OR immunological reaction (rash or  $> 5\%$  eosinophilia)

Then:

- a) Interrupt study medication
- b) Initiate drug-induced liver injury work-up for alternative etiologies
- c) Repeat liver profile (AST, ALT, total bilirubin, direct bilirubin, ALP) and PT or INR within 48 to 72 hours

- d) Monitor the patient using close observation found in [Section 10.2.2.2](#)
- e) If a patient lives in a remote area, they may be tested locally and the results communicated to the investigator site promptly

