#### **10.2.3 Demographics/Medical and Surgical History**

Demographic information per country regulations (age, full date of birth, gender, race, and ethnicity), along with medical and surgical history, will be obtained and recorded in the eCRF at Visit 1.

Medical and surgical history will be entered in the eCRF at Visit 1. This includes date of diagnosis of PFIC, prior investigational medications for PFIC, historical (3 months prior to Screening) LFT values (AST, ALT, and total bilirubin), ongoing medication, any surgery performed, any other diagnosis, and historical biopsy data.

If a liver biopsy has been performed within 1 year prior to Screening, or during the study, the results will be recorded in the eCRF.

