**Table 2 Schedule and Volumes of Blood Sampling**

	Screening	Screening	Random ization	4 weeks	8 weeks	12 weeks	18 weeks	22 weeks	24 weeks	FU	Total blood volume
Study Days	-56 – (-14) ±2	-28 – (-7) ±2	0	28 ±3	56±3	84±3	126 ±3	154 ±3	168 ±3	196 ±3	
Study Visits	Visit 1	Visit 2	Visit 3	Visit 4	Visit 5	Visit 6	Visit 7	Visit 8	Visit 9/EOT	Visit 10	
Hematology test (EDTA)		1	1	1	1	1	1		1	1	8
Clinical chemistry test (SST) a		2.5	2.5	2.5	2.5	2.5	2.5		2.5	2.5	20
Pregnancy		0									0
INR		2		2		2		2		2	10
Serum bile acid	2.5	0	0	0	0	0	0	2.5	0	0	5
Blood sample for genetic testing	3										3
Serum growth marker (IGF-1)			2						2		4
Autotaxin			1 a	1 a					1 a		3
p-C4 (7 $\alpha$ -hydroxy-4-cholesten-3-one)			2 a	2 a					2 a		6
hsCRP		0	0	0	0	0	0		0	0	0
LDL-C		0		0					0		0
Alfa-fetoprotein (AFP)		0		0					0		0
Total amount of blood for children >5 kg	5.5	5.5	5.5	5.5	3.5	5.5	3.5	4.5	5.5	5.5	50
Total amount of blood for children >10 kg	5.5	5.5	8.5	8.5	3.5	5.5	3.5	4.5	8.5	5.5	59

Note: All blood volume presented in mL. All samples of 0 mL are included in the clinical chemistry test (SST).

CRP: c-reactive protein; EDTA: ethylenediaminetetraacetic acid; EOT: end of treatment; FU; Follow-up; INR: international normalized ratio; SST: serum-separating tube

a Not collected for children  $\leq$  10 kg.

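### Entry limits name only ALT and bilirubin while interruption applies to ALT or AST, so a child can be eligible and already meet an interruption criterion

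*Protocol*

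**What the plan says.** **Entry.** Section 7.2.2 excludes a child with ALT above 10 × ULN at Screening (criterion 12), with ALT above 15 × ULN "at any time point during the last 6 months unless an alternate etiology was confirmed for the elevation" (criterion 13), or with total bilirubin above 5 × ULN at Screening (criterion 14). No exclusion names AST. Criterion 22 is a general discretionary exclusion.

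**Interruption.** Section 10.2.2.1 interrupts study drug if any one of six criteria is met. Criterion 1 is ALT or AST at 3 × baseline or 800 U/L, together with total bilirubin above 2 × ULN. Criterion 2 is ALT or AST above 10 × ULN, or at 5 × baseline, "or absolute threshold of 800 U/L, whichever comes first) in presence of normal LDH and CPK".

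**Which samples decide.** Section 7.1.1 (Treatment Period) says eligibility is determined at Visit 3 from the scratching data, "genetic confirmation of diagnosis, and the liver biochemistry evaluations from the previous screening visits". Table 1 and Section 7.1.3.1 schedule clinical chemistry at Visit 1 and not again until Visit 3. The Visit 2 list ("A second Screening Visit will be performed. Screening procedures and assessments are as follows") has urinalysis, s-BA, INR, vitamins A and E and a pregnancy test, but no ALT, AST or bilirubin. At Visit 3 chemistry is drawn, drug is dispensed, and dosing starts on Day 1.

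**History.** Section 10.2.3 records "historical (3 months prior to Screening) LFT values (AST, ALT, and total bilirubin" among the medical history items.

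**The concern.** Limits for entry and for interruption should be compatible: a child who qualifies should not, on the same values, already satisfy a rule that stops the drug. Two features break that here. AST counts for interruption but not for entry. In addition, the 800 U/L and 10 × ULN limits are absolute, so a child who has been stable above them for months meets them without any change on treatment.

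A child randomized in this position joins the full analysis set on the first dose (11.2.1) and is not replaced if withdrawn (7.2.3), in arms of about 20. Interruption would follow from a value present at entry and could be mistaken for a drug effect on the liver. The issue concerns patient protection first, and dosing in small arms second.

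The look-back mismatch is a separate inconsistency: the eCRF history covers a shorter period than the criterion that it would help to document.

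**Working it through.** **1. Limits side by side**

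| Marker | Named entry limit (7.2.2) | Interruption limit (10.2.2.1) |
|---|---|---|
| ALT | excluded if >10 × ULN at Screening, or >15 × ULN in the last 6 months (with an exception) | criterion 1: ≥3 × baseline or 800 U/L, with bilirubin >2 × ULN; criterion 2: >10 × ULN, 5 × baseline or 800 U/L, with normal LDH and CPK |
| AST | none | same as ALT |
| Total bilirubin | excluded if >5 × ULN | >2 × ULN, as the second part of criterion 1 |

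**2. AST, route through criterion 1.** Take AST 800 U/L, bilirubin 3 × ULN, ALT not above 10 × ULN. Exclusions 12 and 13 do not apply, and 3 ≤ 5, so exclusion 14 does not apply. Criterion 1 is met, since 800 ≥ 800 and 3 > 2. The same holds for any bilirubin above 2 and up to 5 × ULN. This route has no LDH or CPK condition.

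**3. AST, route through criterion 2.** Take AST 12 × ULN, ALT 9 × ULN, LDH and CPK normal. Exclusion 12 does not apply, since 9 ≤ 10. Criterion 2 is met, since 12 > 10. Creatine kinase is in Table 3 but LDH is not, so the scheduled laboratory tests alone cannot confirm this route.

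**4. ALT.** Entry allows up to 10 × ULN and criterion 2 begins above 10 × ULN, so the ratio of the two limits is 10/10 = 1 and there is no margin. The qualifying value cannot itself meet the >10 × ULN part of criterion 2, but any rise past it does, given normal LDH and CPK. An eligible ALT reaches 800 U/L only where ULN is at least 800/10 = 80 U/L; the protocol gives no ULN.

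**5. Age of the qualifying sample.** The plan's own figure is "The study includes a 35- to 56-day Screening Period followed by a 24-week Treatment Period". Table 1 puts Visit 1 at Day -56 to -35, ±2 days:
- shortest: 35 − 2 = 33 days before Day 0;
- longest: 56 + 2 = 58 days before Day 0.

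No text makes randomization or the first dose wait for the Day 0 chemistry.

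**6. Look-back.** Six months is 182.6 days and three months is 91.3 days.
- Counted back from Visit 1: 91.3/182.6 = 50% of the period is covered.
- Counted back from Day 0, adding the screening interval: (91.3 + 33)/182.6 = 68% to (91.3 + 58)/182.6 = 82%.

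**The case against.** **The wording in 7.1.1 may be accurate.** Liver biochemistry can be read to include s-BA, drawn at Visits 1 and 2, and INR, drawn at Visit 2. Exclusions 12 and 14 say only at Screening, which Visit 1 satisfies. This reading is fair, so the plural alone proves no contradiction. What stands is that for ALT and bilirubin there is one scheduled sample, and 7.1.1 does not say so.

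**Criterion 2 needs LDH, and the protocol softens the gap elsewhere.** LDH is outside Table 3, so a child stable at AST 12 × ULN might never be shown to meet criterion 2. That weakens the second AST route but leaves criterion 1 untouched. Review of the criteria at Visit 3, exclusion 22 and extra visits all help, but none requires an AST check or a newer ALT or bilirubin value. Re-challenge (10.2.2.3) may be considered once liver tests are back at baseline. For this child, baseline is itself a value that meets the limit.

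**Stronger readings that the documents do not support.**
- *A probability of interruption.* A reader might assume a within-patient CV of 10% to 40% for ALT with no trend. For a Visit 1 value of 9 × ULN, with s = √ln(1 + CV²), the chance of exceeding 10 × ULN at Day 0 is 1 − Φ(ln(10/9)/(s√2)), or 0.23 to 0.42. But the protocol gives neither the CV nor the distribution of entry ALT, and this is the chance of crossing the ALT limit, not of interruption, because LDH and CPK are ignored.
- *Exclusion 13 cannot be verified.* Section 13.2 gives the monitor access to hospital and clinical records, and 15.1 requires laboratory reports and medical history to be kept. Section 10.2.3 governs what is entered in the eCRF, not what a site may consult.
- *The 3- versus 6-month mismatch leads to interruption.* It does not; it concerns past ALT only.
- *Visit 2 chemistry would need no extra blood.* The September 2017 blood table notes "All samples of 0 mL are included in the clinical chemistry test (SST", but that table is superseded and omits vitamins A and E, which Visit 2 now includes.

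**Conclusion.** The mismatch is real and should be resolved. Through AST, a child can pass every named entry limit and meet interruption criterion 1, or criterion 2 if LDH and CPK are normal, with no change on treatment; only discretionary exclusion 22 could prevent it. For ALT the two limits coincide, and the deciding sample is 33 to 58 days old at randomization. These conclusions need no assumption about variability. Their frequency, and any effect on the primary endpoints, cannot be derived from the protocol. The look-back mismatch stands as a separate, smaller inconsistency. The point rests on the protocol text dated 6 December 2017, whose repeated copies agree on these rules; differences in the September 2017 version are not counted as errors, and a later version may exist that is not shown.

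**What to change.** Reconcile three pairs of passages:

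1. Exclusions 12 to 14 (7.2.2) with interruption criteria 1 and 2 (10.2.2.1), so that both address the same transaminases and a child cannot qualify and meet an interruption criterion on the same values.
2. Section 7.1.1 (Treatment Period) with Table 1 and 7.1.3.1, stating which chemistry sample or samples decide eligibility and what part, if any, the Day 0 result plays.
3. The look-back in exclusion 13 with the window for historical liver tests in 10.2.3.

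Which limits, samples and windows apply is for the sponsor to decide. The cost is a protocol amendment with a few wording changes, and possibly a few more screen failures.
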